3 STUDY DESIGN

3.1 Overall Design

Study design: This is a prospective, interventional study with a primary objective of evaluating severe acute respiratory syndrome coronavirus 2 (SARS-CoV-2) transmission following exposure in Kindergarten through 12th grade school students and staff. Participants will be tested with a COVID-19 testing kit that is Food and Drug Administration (FDA)-authorized under an emergency use authorization (EUA) for non-prescription use for both symptomatic and asymptomatic evaluation in children and adults. During the initial phase of this study, participants who consent to participate in this study will be tested at days 1, 3, 5, and 7 following a known COVID-19 exposure on day 0. If a participant does not know of the exposure until more than one day following the exposure, they will be tested on the day they become aware of the exposure and then resume the aforementioned testing schedule (e.g. participant identifies exposure 3 days after the exposure, test on day 3, day 5, and day 7). After the initial phase, the number of tests may be reduced and the test time points may change based on analysis of current data. All modifications will be made only if deemed safe by the safety monitoring committee and NCDHHS.

If the COVID-19 tests are negative, the participant will remain in the school environment. A positive COVID-19 test or the development of symptoms on any day after exposure would require isolation according to school, local and state guidelines. Demographic information, daily presence or absence of symptoms, whether the infected person or close contact was masked, setting of the exposure, test results, and school absences will be collected following consent. Data regarding school level mitigation practices will also be collected. Data collected from this study may be combined with school-provided data and publicly available community data.

3.2 Study Definition of Enrollment

Study enrollment is defined as the participant has provided informed consent (or assent) and completed at least one day of testing in an effort to avoid quarantine.

3.3 Study Definition of Completion

An individual will complete the study after completing all testing days and symptom monitoring (up to 14 days), or data entry that explains why all testing was not completed (e.g., positive test, symptoms, quarantine).

4 STUDY POPULATION

4.1 Selection of the Study Population

4.1.1 Inclusion Criteria

1. Consent completed
2. Child or adult that is part of a school community
3. Known exposure to SARS-CoV-2

4.1.2 Exclusion Criteria

There are no exclusion criteria for this study, all inclusion criteria must be met for participation. Some restrictions to inclusion may apply based on school-specific policies (e.g., optional masking).

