Yet, current policies and procedures requiring quarantine after close contact exposures to limit further spread have led to hundreds of thousands of missed school days and have threatened the school workforce, greatly impeding school operations and the ability of children to appropriately learn. In the fourth quarter of 2021 in NC alone, more than 40,000 students and staff were required to quarantine as a result of being a close contact of a COVID-19 case (unpublished). Fortunately, recent CDC and local guidance have eliminated quarantines for most exposed, unvaccinated, asymptomatic children who are wearing a mask and who are in close contact with another masked, infected child within the classroom setting. However, many quarantines continue to result in unvaccinated adults, children exposed to infected adults, and masked exposures occurring outside of the classroom (e.g., athletics or busing). Moreover, schools and local governments are steadily lifting mask mandates, even as local community cases rise, contributing to exponential increases in quarantines that not only keep children and staff out of schools and parents out of work, but have often overwhelmed school resources and the public health system.

To address the issue of quarantines while ensuring that the school and surrounding community remain safe from SARS-CoV-2 spread, some locales have begun implementing a "test to stay strategy", whereby a close contact undergoes serial testing over a specified duration of time.

The close contact must wear a mask during this time period but is not required to undergo quarantine as long as the screening tests remain negative and the contact remains asymptomatic. While this strategy is supported by strong scientific premise and initial data are promising, the impact of this strategy on quarantine, and secondary and tertiary within-school transmission has not been systematically evaluated.

This study will partner with schools to allow students and staff to remain in school following exposure if they continue to test negative for COVID-19 over pre-determined intervals. This study aims to collect data to assess the spread of SARS-CoV-2 in school communities with varying mitigation strategies to provide data-backed guidelines for mitigation strategies in schools. The study team will work with NCDHHS and a safety monitoring team on a weekly basis to interpret data, evaluate safety, and design next steps (e.g. testing frequency and timing).

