8.1.2 Secondary Endpoints

Secondary Objective #1: Characterize the effect of individual-level masking on SARS-CoV-2 spread.

Secondary #1 Endpoints:

- Proportion and number of masked students with positive COVID-19 test who were exposed to SARS-CoV-2 from masked versus unmasked individuals.
- Proportion and number of masked staff with positive COVID-19 test who were exposed to SARS-CoV-2 from masked compared to unmasked individuals
- Proportion and number of unmasked students with positive COVID-19 tests who were exposed to SARS-CoV-2 from masked compared to unmasked individuals
- Proportion and number of unmasked staff with positive COVID-19 tests who were exposed to SARS-CoV-2 from masked compared to unmasked individuals

Secondary Objective #2: Characterize the effect of exposure setting on SARS-CoV-2 spread.

Secondary #2 Endpoints:

- Proportion and number of students with positive COVID-19 test after indoor vs. outdoor exposure.
- Proportion and number of students with positive COVID-19 test after athletic vs. classroom exposure.
- Proportion and number of students with positive COVID-19 test after bus vs. classroom exposure.

Secondary Objective #3: Describe COVID-19-related school absences for up to 14 days following within-school SARS-CoV-2 exposure.

Secondary #3 Endpoints:

- Total number of school days missed due to symptoms after exposure.
- Total number of school days missed due to isolation after positive COVID-19 test.
- Total number of school days missed due to quarantine after SARS-CoV-2 exposure.

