8.2.2 Secondary Analysis

The proportion and number of students/staff who reported masking and unmasking will be reported and presented in graphical form. The primary analysis will be repeated for masked and unmasked participants (students and staff) separately. The primary analysis will be repeated for masked and unmasked source of exposure separately.

School absences will be analyzed by absences due to symptoms, positive COVID-19 test, or due to quarantine for exposure to SARS-CoV-2. To account for the within-school correlation of outcomes, analyses will be conducted using a generalized estimating equations approach using a loglink suitable for count outcomes, with a working independence correlation structure.

To account for within-school correlation, a risk between the schools using a generalized estimating equation approach with an identity link and a working independence correlation structure will be estimated. The risk difference will be estimated for each semester during the study period, as well as overall. Students will be censored by end of data or study withdrawal. Censoring will be addressed by incorporating inverse-probability censoring weights into the regression model, with censoring risk estimated with a Kaplan-Meier estimator.

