1.6 Secondary Analysis

- Objective: The proportion of students/staff who reported masking and unmasking will be summarized and presented in a bar chart to see the trend by testing day.
 - The primary analysis will be repeated for masked and unmasked participants (students and staff) separately.
 - The primary analysis will be repeated for masked and unmasked source of exposure separately.
- Objective: School absences will be analyzed by absences due to symptoms, positive COVID-19 test, or due to quarantine for exposure to SARS-CoV-2.
 - To account for the within-school correlation of outcomes, analyses will be conducted using a generalized estimating equations approach using a loglink suitable for count outcomes, with a working independence correlation structure (Zeger et al. 1988).

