2.2 Data

TTS data collected from K-12 students and staff with a non-household, within or outside of school exposure to SARS-CoV-2 between November 29, 2021 and January 28, 2022 under school districts in North Carolina (NC) employing optionally masking.

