3.2 Data

TTS data collected from K-12 students and staff with household exposures within 4 districts and 1 charter school in North Carolina (NC) employing universal masking.

- Establish population cutoff
 - [name] (Statistical programmer): Here are the number of household exposures with test results on or after days 5, 7, and 9: \geq Day 5 = 282; \geq Day 7 = 251; \geq Day 9 = 214
 - [name] (Project leader): Given that ~65% of population made it into analysis eligible population for day 9, we will use this day as the cutoff, which is consistent with CDC guidance for household close contacts

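### The planned masking comparison runs across schools, so the individual masking effect sought in secondary objective 1 is mixed with school mask policy and local spread

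*Protocol*

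**What the plan says.** Protocol 8.1.2 words secondary objective 1 as an effect: "Characterize the effect of individual-level masking on SARS-CoV-2 spread". Its endpoints cross-classify: among masked participants, and again among unmasked participants, positivity after exposure to a masked versus an unmasked source, for students and staff separately. SAP 1.3 does not carry this over. Under Secondary #1 it lists the four primary endpoints again.

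The analysis in SAP 1.6 is: "The primary analysis will be repeated for masked and unmasked participants (students and staff) separately". Protocol 8.2.2 has the same sentence and adds, as SAP 1.6 also does: "The primary analysis will be repeated for masked and unmasked source of exposure separately". The analysis being repeated (protocol 8.2.1, SAP 1.5) is a proportion with a 95% interval from GEE with working independence. SAP 1.5 gives it overall, for students and staff, and by district and school level. Protocol 8.2.1 adds a weekly graph. No masking analysis names a covariate, stratum or matching factor.

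On the schools:
- Protocol 1.1.1 aims to "assess the spread of SARS-CoV-2 in school communities with varying mitigation strategies", and says mask mandates were being lifted while community cases rose.
- Protocol 3.1 states: "Data regarding school level mitigation practices will also be collected". It also allows linkage to community data. Neither source enters a Manuscript 1 analysis.
- SAP 2.2 takes its data from participants "under school districts in North Carolina (NC) employing optionally masking". SAP 3.2 takes household exposures "within 4 districts and 1 charter school in North Carolina (NC) employing universal masking".
- Protocol 4.1.2 says "Some restrictions to inclusion may apply based on school-specific policies (e.g., optional masking".

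**The concern.** Where masks are required, few people should be unmasked at exposure. Unmasked participants and sources would then come mainly from schools where masking is optional. Those schools can also differ in how many others wear masks, in other mitigation, and in community incidence on the exposure date. A gap between the overall masked and unmasked proportions can then appear with no individual effect of masking, and a real effect can be enlarged, hidden or reversed.

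Protocol 1.1.1 says the study is meant to inform mitigation guidance for schools, so readers are likely to take the contrast as causal. Enrolment of up to 1,000,000 (protocol 8.3) does not help: a larger sample narrows the interval around the same mixed quantity.

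**Working it through.** **No plan figure to reproduce.** Protocol 8.3 reports no sample size calculation, and neither document gives masking rates or risks by mask policy. All inputs below are assumptions that show the mechanism.

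**1. Pooled risks.** Let w be the share of participants in universal-mask schools, mU and mO the masked shares in universal- and optional-mask schools, and rU and rO the risks, the same for masked and unmasked people (no mask effect).

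- Masked: pM = [w·mU·rU + (1−w)·mO·rO] / [w·mU + (1−w)·mO]
- Unmasked: pN = [w(1−mU)·rU + (1−w)(1−mO)·rO] / [w(1−mU) + (1−w)(1−mO)]

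Take w = 0.5, mU = 0.95, mO = 0.20, rO = 0.05.

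- Half the risk under universal masking (rU = 0.025): pM = (0.475×0.025 + 0.10×0.05)/0.575 = 0.0293; pN = (0.025×0.025 + 0.40×0.05)/0.425 = 0.0485. Ratio 0.60.
- Double the risk (rU = 0.10): pM = (0.475×0.10 + 0.10×0.05)/0.575 = 0.0913; pN = (0.025×0.10 + 0.40×0.05)/0.425 = 0.0529. Ratio 1.72.
- Equal risk (rU = 0.05): both 0.0500. Ratio 1.00.

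**2. Other masked shares** (w = 0.5, true ratio 1):

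| Masked, universal / optional | Universal has half the risk | Universal has double the risk |
|---|---|---|
| 95% / 20% | 0.60 | 1.72 |
| 95% / 50% | 0.70 | 1.52 |
| 80% / 40% | 0.76 | 1.33 |
| 50% / 50% | 1.00 | 1.00 |

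With a true ratio of 0.70 and 95%/20% masked, the pooled ratio runs from 0.42 to 1.21 over the same two risk settings.

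**3. What GEE does.** A simulation fitted the risk difference by GEE with identity link, working independence and school-clustered variance. It used 50 participants per school, 95%/20% masked, 5% risk in optional-mask schools, a between-school coefficient of variation of 0.5, no mask effect, and 1,000 runs.

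| Schools | Risk, universal vs optional | Unadjusted mean difference | Unadjusted 95% coverage | Coverage adjusted for school's masked share |
|---|---|---|---|---|
| 60 | half | −0.020 | 32% | 95% |
| 200 | half | −0.019 | 1% | 94% |
| 60 | double | +0.039 | 10% | 94% |
| 200 | double | +0.038 | 0% | 95% |

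With equal risks the unadjusted coverage was about 95%. The clustered variance was doing its job. The unadjusted estimator was aimed at a mixture of within-school and between-school differences.

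**4. Limits of the check.** The simulation has one calendar period and models the participant's own masking only. For the source contrast in protocol 8.1.2 the same algebra applies within masked (or unmasked) participants, with m as the share exposed to a masked source. The documents give no inputs for that either. The plan itself specifies no masked-minus-unmasked difference. The simulated difference is the one a reader would form from the two proportions.

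**The case against.** The strongest reply is that the plan does not rest on one pooled figure for each masking group. If repeating the primary analysis carries over every breakdown in SAP 1.5, masked and unmasked proportions also appear by district, which is mainly the level at which the SAP describes mask policy. Under protocol 8.2.1 they would also appear by week. This stands: a reader who infers that only a single pooled comparison is planned would be wrong. But these are separate descriptive displays. The district rows do not account for time, the weekly graph is not within school, and no combined within-school estimate follows. The risk difference by semester in protocol 8.2.2 is described as between schools and does not mention masking.

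Three further limits on the point also stand:
- A reader might take SAP 3.2 as proof that universal-mask records sit in the masking analysis. It shows that such districts took part, but its records are household exposures, and SAP 1.2 limits Manuscript 1 to exposures in the school setting.
- A reader might treat protocol 4.1.2 as the source of the problem. It says only that school policy may restrict inclusion, not who is restricted. The gap is in protocol 8.2.2 and SAP 1.6.
- No test, difference or ratio is specified, so the results could be called descriptive. That would be coherent, but objective 1 asks for an effect and would be left unanswered.

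**Conclusion.** The point holds for secondary objective 1. The overall masked versus unmasked comparison cannot separate individual masking from school policy and local spread, and working-independence GEE does not change that. The primary endpoints are not affected.

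The size is unknown. The assumed illustration gives a spurious pooled ratio anywhere from 0.60 to 1.72, and exactly 1 if either the risk or the masked share is the same under both policies. That masking follows school policy is an inference. It is natural under a mask requirement, but neither document gives rates. A reader might go further and conclude that the plan will make masks look better than they are. The documents do not support that: they do not say which schools had the higher risk, and the bias can go either way.

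**What to change.** In protocol 8.2.2 and SAP 1.6:

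1. Keep the overall and by-district proportions, labelled as description.
2. Add a masked versus unmasked contrast for the participant's masking. Within masked and within unmasked participants, add the contrast for the source's masking, so that the protocol 8.1.2 endpoints are addressed. Restore those endpoints in SAP 1.3.
3. Stratify each contrast by school (by district where schools are sparse) and calendar period. A Mantel-Haenszel risk difference with school-clustered variance would serve, or a GEE adjusted for the school's masked share and period.
4. Base the statement on objective 1 on this contrast.
5. Where the school-level mitigation data give the mask policy in force, report universal-mask and optional-mask schools in separate rows. Protocol 3.1 does not say that policy is recorded by date, so this step may be possible only in part.

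The cost is wording and modest extra analysis. Participant and source masking are already collected at enrolment (protocol 5.3). Strata with one mask status or no events add little or nothing, so the interval will be wider. Confounding within a school remains, for example by exposure setting: protocol 1.1.1 notes that masked exposures outside the classroom still led to quarantine, while most masked classroom exposures between children did not. The report should state this limit.

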4.2 Participant Discontinuation/Withdrawal

A participant or his/her parent (or legal guardian) may voluntarily withdraw consent to participate in the study at any time. Participants are not obligated to state the reason for withdrawal. No additional study data will be collected after consent has been withdrawn, however, all data collected prior to consent withdrawal will be maintained in the database.

4.3 End of Study

Participants will be considered off study at the end of the school semester in which they enrolled onto the study.

5 STUDY PROCEDURES

5.1 Summary of Evaluations

	Enrollment/Baseline	Testing Period	Follow-Up
PROCEDURE	Day 0	Day 1, 3, 5, 7	Up to Day 14
Screening	X		
Informed consent/assent	X		
Confirm eligibility criteria	X		
Demographics	X		
Mitigation data collection	X		
Exposure information	X		

COVID-19 testing and results collection		X	
Symptom data		X	X
Safety Assessment		X	

5.2 Screening Questions

Several screening questions will be asked via REDCap prior to consent to assure the correct consent is assigned to the person completing the form (e.g. parent/adult consent, or consent/assent combination). These screening questions ask about language preference (e.g. English or Spanish), and the age of the person who had a within-school COVID-19 exposure (e.g. less than 7 years of age, between 7 and 17 years of age, and 18 years of age or older). No identifiable information will be collected until after informed consent has been obtained. These questions will be used for screening purposes only.

5.3 Enrollment/Baseline

Participants or their parent/legal guardian will provide informed consent (or assent). Applicable informed consent from the participant or parent/legal guardian (and assent if applicable) for all participants will be documented. After consent, the participant will be assigned a unique ID by the school nurse or administrator. The school nurse or administrator will collect study-related variables via a spreadsheet using one of two different methods. The school nurse may use AirTable, a system designed by Technology and Data Solutions, or standard excel spreadsheets, which will be sent to the research team. The research team will have access to individual-level data but will not have access to names or other identifiers. While the study team will have access to the consents completed via REDCap, the team will not know which unique ID belongs to which individual.

The following information will be collected from the student at the time of enrollment. Information may be collected directly from the participant, their parent/legal guardian, or via a school nurse. The information will include the following:

- Participant demographics (age, sex, English proficiency, and vaccination status)
- Mitigation data collection including whether the participant was masked or unmasked, and vaccination status (if known)
- Exposure details include when exposure occurred, where it occurred, and if the individual who caused the exposure was masked or unmasked

5.4 Testing Period

Eligible participants will undergo COVID-19 testing on days 1, 3, 5, and 7 following known SARS-CoV-2 exposure. If a participant is not aware of the exposure until after the day of exposure, testing will begin immediately on the day of exposure awareness and then resume according to the study schedule (see **Table 1** below for examples). Testing will occur at home or at school according to the Instructions for Use. Participants will be asked to report symptoms for during the testing period. Safety and testing results will also be collected. Pending approval from NCDHHS, the number of tests and the test time points may be changed if deemed safe based on analysis of prior data. For example, if these stakeholders agree that the Test to Stay protocol is safe with two tests rather than four, this change in test frequency may be made. When designing this protocol, the study team used a very conservative approach to prevent undue harm to participants. Over the next several weeks and months, the study team will work closely with stakeholders to modify the test time points and total tests performed to identify the optimal testing protocol which is sustainable for schools (time, resources) but also deemed to be safe.

Table 1. Testing Schedule based on knowledge of exposure

Exposure day	Knowledge of exposure day	Testing days
0	0	1, 3, 5, 7
0	1	1, 3, 5, 7
0	2	2, 3, 5, 7
0	3	3, 5, 7
0	4	4, 5, 7
0	5	5, 7

5.5 Follow-Up

Participants will be asked to report symptoms for up to 14 days following SARS-CoV-2 exposure. Schools will be asked to report tertiary spread and number of close contacts for individuals who tested positive.

